After each subject has completed visit 4 follow-up assessments (7 days after drug administration), the dosing investigator will complete the 'DLE Safety Review Form' to summarise the key safety findings for the subject. Once completed, the site will send the form to the CTM and CTL.

First 2 subjects in cohort 1 ([REDACTED])

Once the first two subjects have attended visit 6 (day 29), each dosing investigator will complete the 'Ocular Inflammation Review forms'.

Subsequent subjects in part A

Once the following subjects have attended visit 5 (day 15), each dosing investigator will complete an 'Ocular Inflammation Review form' to identify any ocular inflammation. Once completed, the site will send the form to the CTM and CTL. Once the last subject in each cohort has attended visit 5 (day 15), the CTL will forward the 'DLE Safety Review Forms' and the 'Ocular Inflammation Review Forms' for that cohort to other members of the SMC to carefully evaluate all available systemic (i.e. physical examinations, safety lab parameters, ECG and AEs) and ophthalmological (i.e. as defined in section 5.2.1 of the CTP (DLEs)) safety data. The SMC will meet after the last subject of each dose cohort has attended visit 5.

A Bayesian logistic regression model (BLRM), based on a weakly informative prior distribution, and employing the escalation with overdose control (EWOC) principle (see Section 7) will be used for guiding the dose escalation [R13-4803]. After all subjects in a cohort have either experienced a DLE or have been observed for at least the 7 days evaluation period without experiencing a DLE (i.e. 7 days after drug administration, until visit 4, will be evaluated per subject), the BLRM will be updated with the newly accumulated data. The overdose risk will then be calculated for each dose, and escalation will be permitted to all planned doses which fulfil the EWOC criterion and the respective escalation rule.

The BLRM provides estimates for the probability of observing a DLE for each planned dose. Dose escalation will be permitted to the next planned dose which fulfils the EWOC criterion. Note that this may also result in repeating the current dose level, or in going down to a lower dose level again.

If DLEs are observed in the first two consecutive subjects of a previously untested dose level, subsequent enrolment to that cohort will be stopped.

The MFD may be considered reached if all of the following criteria are fulfilled:

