3.2 DISCUSSION OF TRIAL DESIGN, INCLUDING THE CHOICE OF CONTROL GROUP(S)

This trial is designed to confirm that the highest dose of BI765128 can be used for further testing in phase IIb trials. The trial consists of separate parts, A and B. The SRD dose escalation part is included and was designed with the goal to minimize the number of subjects exposed to subtherapeutic doses while on the other hand preserving safety and rapid dose finding. This part of the trial will enrol subjects with DMI as IVT injections in healthy subjects would not be considered ethical. Dose escalation and cohort size will be decided by the SMC, guided by a BLRM with overdose control. An EWOC design will increase the chance of treating subjects at efficacious doses while reducing the risk of overdosing. The use of BLRM for Phase I studies has also been advocated by the European Medicines Agency (EMA) guideline on small populations [[R07-4856](#)] and by the Food and Drug Administration (FDA) [[R13-4881](#)].

Part B will consist of a MD cohort [REDACTED] and will start after Part A. Subjects will either be randomized to the active treatment group or to a sham control group (ratio 2:1). This part of the trial will generate additional safety data after multiple dosing and allow for exploration of the time course and durability of treatment effects. This data will further inform the injection frequency and intervals in later studies.

An extended SMC will be established for both part A and part B. The SMC shall operate under the principles specified in the SMC charter. The primary objective of the SMC is to ensure and protect the safety and well-being of the trial subjects and to regularly review the trial data and provide recommendation for the further conduct of the trial (see section [8.7](#)).

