3.3.5 Replacement of subjects

Part A:

Subjects withdrawn before visit 4 for another reason than DLE or subjects who miss any visit from Visit 2 up to and including Visit 4 are not evaluable for the occurrence of a DLE within 7 days after drug administration. These subjects will be replaced if not decided otherwise by the SMC. Subjects who come off study due to a DLE will not be replaced.

Part B:

If some subjects do not complete the trial, the Clinical Trial Leader together with the Trial Pharmacokineticist and the Trial Statistician are to decide, if and how many subjects will be replaced. A replacement subject will be assigned a unique trial subject number and will be assigned to the same treatment as the subject he or she replaces.

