4.1.6 Masking and procedures for unmasking

4.1.6.1 Masking

Part A of the trial is open label. Part B is designed double-masked. The treatments administered (active or sham injection) will be masked to subjects and to the dedicated personnel of the trial site. The table below summarizes the masking level of individual functions in Part B of the trial.

Table 4.1.6.1:1 Overview about masking status of trial role and functions in Part B

Role/function	Timing of Unmasking / receiving access to the treatment information (including rationale)
Subjects	Masked until data ready for final analysis.
Investigator/Site staff	Masked until data ready for final analysis.
Pharmacist*	Unmasked during trial conduct.
Injector**	Unmasked during trial conduct
Sponsor (incl. clinical trial/project team) SMC and database	Unmasked descriptive analyses will be performed on the subjects in the database during the trial conduct (see Section 7.3.7). The release of the treatment information at the individual time points will be documented accordingly.
Bioanalytical Staff	Unmasked as requested for analysis of bioanalytical samples.

* Unmasked independent pharmacist (qualified person) with no other involvement in the trial will prepare the active IVT injection

** Unmasked independent injector with no other involvement in the trial will administer active/sham injections.

Within the central ECG lab, readers involved with interval measurements will be masked with respect to treatment, visit and demographic information collected. During the time a role/function is masked, the treatment information is kept restricted by the global Randomization Team (gRT) per Sponsor Standard Operating Procedure (SOP).

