7.3 PLANNED ANALYSES

7.3.1 Subject analysis sets

The main analysis populations are defined below. In the TSAP, further analysis data sets may be defined. Subjects will be analysed according to the assigned treatment, unless otherwise specified.

Important protocol deviations (IPD) categories will be defined in the IPD specification document. IPDs will be identified no later than in the Report Planning Meeting, and the IPD categories will be updated as needed. The handling of subjects with IPDs will be described in the TSAP.

Treated set (TS)

For part A the treated set includes all subjects who were treated with at least one dose of study drug.

For part B the treated set includes all subjects who were randomized and treated with at least one dose of study drug (either treatment with BI 765128 or Sham).

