7.3.7 Interim Analyses

No interim analysis is planned.

The sponsor will continuously monitor the safety.

Part A

The dose escalation design of the Part A foresees that the sponsor and the SMC perform regular safety evaluations, the SMC will meet after the last subject of each dose cohort has attended Visit 5 (section [3.1](#)) These evaluations will be unmasked to dose.

Part B

The sponsor and the SMC perform one safety evaluation, the SMC will meet after 50% of the subjects were randomized and finished Visit 5. This analysis will involve descriptive and graphical presentation of primary, secondary and further endpoints. These evaluations will be unmasked to dose.

In addition, a fast track analysis will be performed after the final subject of Part B has attended Visit 6 (i.e. approximately 8 weeks after receiving the final dose).

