7.5 RANDOMISATION

Part A

Subjects within a cohort receive the same trial medication, therefore no randomization for treatment assignment is performed.

Part B

Subjects will be randomized in a 2:1 ratio (BI 765128: Sham injection).

BI will arrange for the randomisation and the packaging and labelling of trial medication. The randomization list will be generated using a validated system, which involves a pseudo-random number generator so that the resulting treatment will be both reproducible and non-predictable. The block size will be documented in the Clinical Trial Report. Access to the codes will be controlled and documented.

The randomization list will contain additional blocks to allow for subject replacement (refer to Section [3.3.5](#)).

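### Could the sponsor's open-ended discretion to replace Part B non-completers distort the FAZ comparison with sham?

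*Protocol*

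**What the plan says.** Protocol 3.3.5 treats the two parts differently. Part A defines who is not evaluable, replaces those subjects unless the SMC decides otherwise, and bars replacement after a DLE. For Part B, three sponsor roles "are to decide, if and how many subjects will be replaced", and each replacement "will be assigned to the same treatment as the subject he or she replaces". Section 7.5 adds: "The randomization list will contain additional blocks to allow for subject replacement". It refers back to 3.3.5 and says that access to the codes is controlled and documented.

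On masking, Table 4.1.6.1:1 keeps subjects and site staff masked until the final analysis. For the sponsor, including the trial team, and the SMC it says: "Unmasked descriptive analyses will be performed on the subjects in the database during the trial conduct", with a reference to 7.3.7. Section 7.3.7 plans one Part B safety evaluation by the sponsor and the SMC once 50% of subjects have been randomised and finished Visit 5: "This analysis will involve descriptive and graphical presentation of primary, secondary and further endpoints. These evaluations will be unmasked to dose". It also plans a fast track analysis after the final Part B subject's Visit 6; SAP 7.5.3 says this presents FAZ area. SAP section 8 loads treatment information once enrolment, meaning randomisation, is complete.

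On analysis, Protocol 7.3.1 says: "For part B the treated set includes all subjects who were randomized and treated with at least one dose of study drug". Treated non-completers therefore stay in the analysis set alongside any replacement.

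**The concern.** A decision on whether to add subjects, taken with outcome data by arm in view, is an optional extension of the sample. If subjects are added only when the FAZ result looks weak, an ineffective drug gets a second chance to show the effect that Protocol 7.6 uses to describe what Part B can detect. With 20 active and 10 sham subjects, a few additions carry weight.

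The text does not exclude this. Section 3.3.5 has no criterion beyond non-completion, no maximum, no latest date and no requirement that the deciders be masked. There is also a question of timing. The last randomised subject can drop out up to Day 141 − Day 1 = 140 days after randomisation, and SAP section 8 does not say whether a later replacement counts as part of the randomisation whose completion releases the codes.

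**Working it through.** **Inputs.** From Protocol 7.6: 20:10 subjects, SD 0.1 mm², an assumed 10% effect, and a 6% threshold given as 0.0462 mm² (hence a base of 0.0462/0.06 = 0.77 mm² and an assumed effect of 0.077 mm²). The documents give no dropout rate, so 1 to 6 non-completers is an assumption. The rule of replacing only if the observed effect is below 6% is also an assumption, chosen as a worst case; 7.6 does not use 6% as a decision criterion.

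**The plan's own figures.** SE = 0.1·√(1/20 + 1/10) = 0.03873 mm².
- True effect 10%: P(observed > 6%) = 78.7% (7.6 prints 81.7%); P(observed < 4%) = 11.6% (prints 10.2%).
- True effect 0%: P(observed > 6%) = 1 − Φ(0.0462/0.03873) = 11.6% (prints 12.3%); P(observed < 4%) = 78.7% (prints 78.7%).

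The 81.7% does not reproduce. That is a separate matter: every comparison below is made within one model.

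**Decision on near-complete data by arm, true effect 0%.** Let D0 be the difference without replacement and D1 the difference with same-arm replacement. The means are nested, so cov(D0, D1) = var(D1). With t = 0.0462, the chance of a result above 6% is P(D0 > t) + P(D1 > t) − P(both > t). For 2 active and 1 sham non-completers whose data are discarded, this is 12.89% + 11.65% − 9.63% = 14.91%.

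| Non-completers (active, sham) | Discarded: none replaced | Discarded: informed | Excess (points) | Retained: none replaced | Retained: informed |
|---|---|---|---|---|---|
| 1, 0 | 11.9% | 12.8% | 0.9 | 11.6% | 12.5% |
| 0, 1 | 12.5% | 14.2% | 1.7 | 11.6% | 13.2% |
| 2, 1 | 12.9% | 14.9% | 2.0 | 11.6% | 13.4% |
| 4, 2 | 14.3% | 17.0% | 2.7 | 11.6% | 13.8% |

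The truth lies between discarding and full retention. Treated non-completers stay in the treated set, and SAP 6.3 censors efficacy data from 28 days after treatment discontinuation, or 1 day after a relevant concomitant medication if earlier. The largest mean bias is 0.00196 mm², and 0.00196/0.077 = 2.5% of the assumed effect.

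**Decision on the planned 50% review.** The same rule is applied to the 10:5 estimate, with the non-completers among the later subjects (simulation). Listed in the same order of non-completers:
- discarded: 11.8%, 12.4%, 12.7%, 14.0%, against 11.9%, 12.5%, 12.9%, 14.3% if none are replaced;
- retained: 11.6%, 11.5%, 11.4%, 11.2%, against 11.6%.

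There is no inflation over never replacing anyone.

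**Which looks can come before a replacement.**
- The 50% review can, and it is harmless on the figures above.
- The fast track waits for the final Part B subject's Visit 6, and a replacement is a Part B subject.
- Code release under SAP section 8 waits for completed randomisation. Protocol 7.5 puts the replacement blocks on the same randomisation list, so the ordinary reading includes them.

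A harmful decision would need either an unplanned look or randomisation reopened after the codes had been released.

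**Whether the same-arm rule is the cause.** Keeping the informed decision but randomising replacements 2:1, with dropouts' data discarded, gives 13.0%, 13.6%, 14.8% and 16.9%. Same-arm assignment gives 12.8%, 14.2%, 14.9% and 17.0%. Changing the assignment method gains nothing.

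**The case for a change.** The strongest argument for a change is that the gap is real, specific to Part B and cheap to close. Part A shows that the authors knew how to write a replacement rule. The sponsor's team is not listed as masked. The Clinical Trial Leader may also sit on the committee that sees results by arm: in Part A the CTL forwards the forms "for that cohort to other members of the SMC", and section 3.2 says: "An extended SMC will be established for both part A and part B". Part B is the only comparison with sham, and FAZ is what the fast track presents. A sentence in 3.3.5 and another in SAP section 8 would remove the question.

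Part of this stands. The documents do not exclude a late, informed decision, and SAP section 8 could say outright that randomisation includes replacements. The committee link is weaker. It rests on a Part A workflow and on reading CTL as Clinical Trial Leader; Part B membership is left to a charter not included here; and nothing comparable is shown for the other two roles. The text also grants a decision on whether and how many to replace, and does not expressly allow a choice by arm. Adding the missing sentences would record what a trial team would ordinarily do, without altering any analysis or estimate.

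**Conclusion.** The observation is correct, but no change follows. Section 3.3.5 leaves a detail unstated that the team can settle sensibly, and the rest of the plan already orders events so that the look which matters comes after replacement. A decision at the planned 50% review does not inflate the FAZ result. The worst case has to be built by assumption: 1 to 6 non-completers, a 6% trigger and near-final data by arm in the deciders' hands. Even then it adds 0.9 to 2.7 percentage points to the chance that an ineffective drug shows more than 6%, with a mean bias of at most 0.002 mm². Part B has no confirmatory test (Protocol 7.2) and its primary endpoint is drug-related adverse events, so no formal decision depends on that margin.

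This conclusion rests on reading completed randomisation in SAP section 8, and the final Part B subject in Protocol 7.3.7, as including replacements. It would weaken if a subject who dropped out after code release were then replaced.

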4. TREATMENTS

4.1 INVESTIGATIONAL TREATMENTS

4.1.1 Identity of the Investigational Medicinal Products

Table 4.1.1: 1 BI 765128

Substance:	BI 765128
Pharmaceutical formulation:	Solution for injection
Source:	Boehringer Ingelheim Pharma GmbH & Co. KG
Unit strength:	[REDACTED]
Posology:	Part A: 1 injection Part B: 3 injections, [REDACTED]
Method and route of administration:	Intravitreal

Table 4.1.1: 2 Diluent

Substance:	Solvent for dilution of BI 765128 solution for injection [REDACTED]
Pharmaceutical formulation:	Solvent
Source:	Boehringer Ingelheim Pharma GmbH & Co. KG
Unit strength:	NA
Posology:	Part A: 1 injection
Method and route of administration:	Intravitreal

4.1.2 Selection of doses in the trial and dose modifications

Three doses [REDACTED] are planned in Part A. Part B will use the highest dose [REDACTED].

BI 765128 was injected intravitreally in New-Zealand White rabbits. Ocular tissues as well as plasma were sampled over a 14-day period and half-lives in the different tissues were

calculated. [REDACTED] and is, thus, also expected to be similar to [REDACTED] in humans. An IVT half-life in humans of 9.7 days has been described for [REDACTED] (R18-2968) and was assumed for BI 765128. The parameters to calculate the minimum effective vitreal concentration were based on the following assumptions: [REDACTED]

Using these values, the proposed therapeutic dose of [REDACTED] mg/eye is predicted to maintain the minimal efficacious vitreal concentration of 1000 pM (1 nM) for three months. Doses lower than [REDACTED] mg are also expected to induce PD effects in the eye. However, the duration of the effect would be shorter and might not provide sufficiently long potential benefit to the subjects.

The proposed escalation of the doses [REDACTED] is predicted to prolong the time for IVT antibody concentrations above the estimated minimally efficacious concentration, potentially allowing for longer dosing intervals. The starting dose and dose escalation were chosen based on the safety margin to the highest tested dose level [REDACTED] mg/eye) that did not result in adverse effects directly attributed to BI 765128, in the 13-week IVT toxicology study in cynomolgous monkeys.

Table 4.1.2: 1 Provisional dose levels for escalation

Dose level	[REDACTED]	[REDACTED]
[REDACTED]	[REDACTED]	[REDACTED]
[REDACTED]	[REDACTED]	[REDACTED]
[REDACTED]	[REDACTED]	[REDACTED]

4.1.3 Method of assigning subjects to treatment groups

After the assessment of all in- and exclusion criteria, subjects will be enrolled into the Part A and Part B. Recruitment in the trial will start with the lowest dose group of Part A. Part B will recruit subjects only after Part A has been completed and safety of the doses has been established.

In Part A, the dose is planned to be escalated in cohorts at the pre-defined provisional dose levels; see Table 4.1.2: 1. Intermediate or lower dose levels, depending on the number of DLEs observed in the study, as long as they fulfil the EWOC criterion, may be investigated if agreed upon between Investigator and Sponsor. At the end of each treatment cohort, BI will convene a meeting with the SMC members. At the dose escalation meeting, all available systemic and ophthalmological safety data (See section 3.1 and 5.2.1) will be reviewed in

detail. Based on that and on the results of the updated BLRM, a decision on the next dose level to be tested is made.

In general, recruitment for Part A will be done successively for the dose groups, i.e. if the required number of subjects for one dose group is completed and this dose is considered safe based on (the BLRM model and the clinical course), the recruitment of the next higher dose group may be started. Therefore, the recruitment of subjects for the dose groups will neither be influenced by the trial personnel nor by any characteristics of the subjects, but only by temporal availability. Subjects from the Part A are not allowed to participate in Part B.

The highest dose (██████), if established as safe and tolerable during Part A will be used in Part B after Part A has been completed. If the highest dose (██████) is not considered safe and tolerable Part B will not commence. In Part B subjects will be randomized to receive either active IVT treatment or sham injection according to a randomization plan at visit 2 via Interactive Response Technology (IRT). 20 subjects will receive IVT treatment and 10 will receive sham injection.

The randomization procedure is described in Section [7.5](#).

4.1.4 Drug assignment and administration of doses for each subject

BI 765128 will be administered intravitreally. “BI 765128 solution for injection ██████” and “Solvent for dilution of BI 765128 Solution for Injection” will be provided by BI. Site personnel who are qualified to prepare IVT injections will prepare the drug product according to the ‘Handling and Preparation Guidelines’. The instructions will be provided by BI and will be filed in the ISF.

Table 4.1.4: 1 Planned doses and treatment schedule for the Part A

Dose group (mg)	Visit 2 Day 1	Visit 3 Day 4	Visit 4 Day 8	Visit 5 Day 15	Visit 6 Day 29	Visit 7 Day 57
██████	██████					
██████	██████					
██████	██████					

To determine the dose regimen for the next cohort, the available information (including DLEs and AEs that are not DLEs) as well as the recommendations from the BLRM will be evaluated by the SMC members at the dose decision meeting. The parties must reach a consensus whether further dose escalation is appropriate, or whether de-escalation and/or expanded recruitment into particular cohorts is appropriate. Minutes from these meetings will be prepared and circulated to the trial team and each investigator for comment prior to finalization. The next dose group will only be initiated after further dose escalation is considered appropriate by the SMC (see Section [4.1.2](#) for details on dose rationale and escalation concept).

Table 4.1.4: 2 Planned dose and treatment schedule for the Part B

Dose group (mg)	Visit 2 Day 1	Visit 3 Day 29	Visit 4 Day 57	Visit 5 Day 85	Visit 6 Day 113

4.1.5 Intravitreal Injection Technique and Sham Injection

IVT injections must be carried out according to medical standards and applicable guidelines by a qualified physician experienced in administering IVT injections. In general, adequate anaesthesia and asepsis, including topical broad-spectrum microbicide (e.g. povidone iodine applied to the periocular skin, eyelid and ocular surface) have to be ensured. Surgical hand disinfection, sterile gloves, a sterile drape, and a sterile eyelid speculum (or equivalent) to be used in accordance with local standards and regulations.

Part B is designed double-masked and personnel of the trial site are masked. Therefore, in Part B, an unmasked injector with no other involvement in the trial will administer IVT/sham injections.

For a sham injection, all pre- and post-injection procedures are identical compared to IVT injections. For a sham injection, the hub of a syringe without a needle is pressed against the conjunctival surface to simulate the force of an actual injection. For sham aqueous sampling, all procedures are identical to aqueous sampling, the hub of a syringe without a needle is pressed gently against the corneal surface to simulate aqueous sampling.

Use of antibiotics in the pre-, peri-, or post-injection period is at investigator's discretion.

After administration of BI 765128, subjects will be monitored according to standard local practice. In this minimum post-dose observation period, systemic and ocular conditions will be monitored according to local practice for such procedures.

